5.1 Grouping Factor

Study Stage: 1=Safety Portion vs 2=Expansion Portion

5.2 Grouping Factor

Disease type: 1=Elderly newly diagnosed AML (assigned treatment Arm A) vs 2=Relapsed/refractory AML vs 3=HMA failure MDS

> NOTE: HMA failure MDS patients include MDS, CMML and MDS/MPN overlap patients. NOTE: Disease type groups 2 and 3 are randomized to arm B or C.

6.0 **Registration/Randomization Procedures**

6.1 Safety Portion

Prior to discussing protocol entry with the patient, call the MCCC Registration Office for dose level and to insure that a place on the protocol is open to the patient.

- 6.11 Registration Procedures
 - 6.111 To register a patient, **Sector a** a completed eligibility checklist to the Mayo Clinic Cancer Center (MCCC) Registration Office between 8 a.m. and 4:30 p.m. central time Monday through Friday.

6.2 Expansion Portion

- 6.12 Registration Procedures
 - 6.121 To register a patient, access the Mayo Clinic Cancer Center (MCCC) web page and enter the registration/randomization application. The registration/randomization application is available 24 hours a day, 7 days a week. Back up and/or system support contact information is available on the Web site. If unable to access the Web site, call the MCCC Registration Office at the text of 8 a.m. and 4:30 p.m. Central Time (Monday through Friday).

The instructions for the registration/randomization application are available on the MCCC web page and confirming patient registration. Prior to initiation of protocol treatment, this process must be completed in its entirety and a MCCC subject ID number must be available as noted in the instructions. It is the responsibility of the individual and institution registering the patient to confirm the process has been successfully completed prior to release of the study agent. Patient registration via the registration/randomization application can be confirmed in any of the following ways:

- Contact the MCCC Registration Office If the patient was fully registered, the MCCC Registration Office staff can access the information from the centralized database and confirm the registration.
- Refer to "Instructions for Remote Registration" in section "Finding/Displaying Information about A Registered Subject."

6.3 Safety & Expansion Portions

6.31 Correlative Research

A mandatory correlative research component is part of this study, the patient will be automatically registered onto this component (see Section 3.17 and 14.0).

- 6.32 Prior to accepting the registration, registration/randomization application will verify the following:
 - IRB approval at the registering institution
 - Patient eligibility
 - Existence of a signed consent form
 - Existence of a signed authorization for use and disclosure of protected health information
- 6.33 Documentation of IRB approval must be on file in the Registration Office before an investigator may register any patients.

In addition to submitting initial IRB approval documents, ongoing IRB approval documentation must be on file (no less than annually) at the Registration Office If the necessary documentation is not submitted in advance of attempting patient registration, the registration will not be accepted and the patient may not be enrolled in the protocol until the situation is resolved.

When the study has been permanently closed to patient enrollment, submission of annual IRB approvals to the Registration Office is no longer necessary.

- 6.34 At the time of registration, the following will be recorded:
 - Patient has/has not given permission to store and use his/her sample(s) for future research of Acute Myeloid Leukemia or Myelodysplastic Syndrome at Mayo.
 - Patient has/has not given permission to store and use his/her sample(s) for future research to learn, prevent, or treat other health problems.
- 6.35 Treatment on this protocol must commence at a participating institution, Mayo Clinic Rochester, Mayo Clinic Arizona, Mayo Clinic Florida, or the University of Colorado, under the supervision of a hematologist.
- 6.36 Treatment cannot begin prior to registration and must begin \leq 14 days after registration.
- 6.37 Pretreatment tests/procedures (see Section 4.0) must be completed within the guidelines specified on the test schedule.

- 6.38 All required baseline symptoms (see Section 10.3) must be documented and graded.
- 6.39a Study drug is available on site.
- 6.39b Blood draw kit is available on site.
- 6.39c Patient questionnaire booklet is available on site; copies are not acceptable for this submission.
- 6.39d Randomization Procedures
 - 6.39d1 The factors defined in Section 5.0, together with the registering membership, will be used as stratification factors.
 - 6.39d2 After the patient has been registered into the study, the values of the grouping factors will be recorded. An elderly newly diagnosed AML patient will be allocated to arm A. A relapsed/refractory AML or HMA failure MDS patient will be randomized to treatment group arm B or arm C.
 - Elderly (age 60+) newly diagnosed AML patients assigned to Arm A: AZD1775 days 1-5, 8-12 and AraC days 1-5, 8-12
 - Relapsed/Refractory AML and HMA failure MDS patients randomized to Arm B: AZD1775 days 1-5, 8-12 and AraC days 1-5, 8-12 or Arm C: AZD1775 days 1-5, 8-12, 15-19, 22-26.

All patients must be registered within 14 days before starting therapy or within 72 hours after starting treatment if over a weekend or holiday. If therapy must be started when the MCCC Registration Office is closed, a telephone call must be made when the MCCC Registration Office is open as indicated above. Under no circumstances will non-registered patients be retrospectively eligible for the study.

7.0 Protocol Treatment

- 7.1 Pre-Treatment Recommendation
 - Pretreatment medication recommendations (this is not a study requirement, but 7.11 simply a recommendation)

Agent	Dose	Route	Day(s)
Ondansetron*	8mg	PO or IV	1-5, 8-12, ^

- *Or serotonin receptor antagonist of institutional standard ٠
- ^ if study drug schedule is days 1-10, give Ondansetron days 1-10

7.2 Treatment Plan for AZD1775 combined with AraC (Arms A and B)

7.21 Safety Portion

The Safety portion of this trial will treat and monitor six patients in each arm and observe them for a minimum of 28 days to assess toxicities.

Starting Doses: Multiple Agent

Agent	Dose	Route	Day(s)	ReRx
AraC ¹	20 mg	SC twice daily ²	$1-5 \& 8-12^3$	Every 28 days ⁴
AZD1775	200 mg	PO daily	$1-5\& 8-12^3$	Every 28 days ⁴

¹ Starting dose of a fixed dose of 20 mg s.c. per a single dose twice daily. In individual cases, a 10 mg/m^2 not to exceed 20 mg can be used alternatively.

²SC administration preferred

³ AZD1775 should be taken either 2 hours before or 2 hours after a meal. A day 1-10 dosing schedule will be permitted as an alternative, in which case AZD1775 should be given days 1-10 as well.

⁴Cycle length can be increased to 6 and maximally 8 weeks

Note: if the starting dose is not tolerated, lower dosing cohort combination will be explored and follow the recommendation as outlined in Section 8.1 Table 8.11.

7.22 Expansion Portion

The Expansion portion of this trial will commence for Arms A and B as soon as the Safety portions for BOTH arms are completed.

Starting Doses

Agent	Dose	Route	Day(s)	ReRx
AraC ¹	20 mg	SC twice daily ²	$1-5 \& 8-12^3$	Every 28 days ⁴
AZD1775	MTD	PO daily	$1-5\& 8-12^3$	Every 28 days ⁴

¹ Starting dose of a fixed dose of 20 mg s.c. per a single dose twice daily. In individual cases, a 10 mg/m² not to exceed 20 mg can be used.

²SC administration preferred

³AZD1775 should be taken either 2 hours before or 2 hours after a meal. A day 1-10 dosing schedule will be permitted as an alternative, in which case AZD1775 should be given days 1-10 as well.

⁴Cycle length can be increased to 6-8 weeks (maximally)

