1.5 Study Design and Treatment

This study is a phase II study testing the clinical efficacy of combined AZD1775 with AraC or single agent activity of AZD1775 in three patient strata: Elderly newly diagnosed AML patients (Arm A) will only receive the combination; whereas relapsed/refractory AML patients and HMA failure MDS patients will be allocated to either the combination (Arm B) or single agent AZD1775 (Arm C). The study will have a run in safety cohort of six patients in each of the three arms to determine the safe use of combined AraC /AZD1775 or single agent AZD1775 in the patient populations. This will be followed by an expansion phase where elderly patients with newly diagnosed AML will receive a combination of AZD1775 and AraC (Arm A) while patients with relapsed or refractory AML or HMA failure MDS will be allocated to receive either AZD1775 with AraC (Arm B) or AZD1775 alone (Arm C). An early toxicity check will be conducted to determine safety and tolerability. If indicated, dose levels will be reduced. The study will continue to enroll the rest of the patients at the tolerated dose.

1.51 Rationale for AraC and AZD1775 Dosing Schedule, Dose Selection and Dosing Arms:

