7.7 MTD Determination

This MTD determination applies to the Safety Portion. MTD for the safety portion will be defined as the dose level below the lowest dose that induces dose-limiting toxicity in at least one-third of patients (at least 2 of a maximum of 6 new patients).

- 7.71 Three patients will be treated at a given dose level combination and observed for one cycle to assess toxicity (accrual will be suspended while the 3 patients are treated and observed).
- 7.72 If DLT is not seen in any of the 3 patients or in 1 of 3 patients, 3 new patients will be accrued. and treated at the same dose level (accrual will be suspended while the 3 patients are treated and observed). If DLT is seen in 2 or 3 of 3 patients treated at a given dose level, then the next 3 patients will be treated at the next lower dose level, if only 3 patients were enrolled and treated at this lower dose level.
- 7.73After enrolling 6 patients on a specific dose level, if DLT is observed in 1 or less patients, then the combination dose will be considered safe for the expansion phase. If DLT is observed in at least 2 of 6 patients, then the MTD will have been exceeded and defined as the previous dose unless only 3 patients were treated at the lower dose level. In that case, 3 additional patients will be treated at this lower dose level.
- 7.75 If a patient fails to complete one cycle of treatment for reasons other than doselimiting toxicity defined adverse events, the patient will be regarded as noninformative for estimating the MTD and an additional patient will be treated at the current dose level.
- 7.8 Dose escalation will not be allowed for a patient.

7.9a For this protocol, the patient must return to the consenting institution for evaluation at least once every 28 days.

7.9b Local Medical Doctor (LMD) When it has been determined that a patient's malignant disease is stable or objective tumor regression has been observed and the patient is tolerating therapy without excessive toxicity, the drug(s) may be administered by the patient's Local Medical Doctor (LMD). The registering physician retains responsibility for the patient.

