In this case, a written statement outlining drug dosage, method of administration, followup tests required, and telephone number to call to discuss any questions with the responsible investigator must be sent with the patient to provide necessary information to the LMD. The LMD will be required to supervise the administration of the study drugs as stipulated in the protocol and provide written documentation that the drug was administered. **8.0 Dosage Modification Based on Adverse Events -** If multiple adverse events are seen, administer dose based on greatest reduction required for any single adverse event observed. Dose modifications apply to the treatment given in the preceding cycle and are based on adverse events observed since the prior dose. Dose modification recommendations listed below are general guidelines, and appropriate dose adjustments for patient safety should be done if needed per treating physician discretion.

ALERT: ADR reporting may be required for some adverse events. See Section 10.0.

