16.0 Statistical Considerations and Methodology

16.1 Overview:

This study is a phase II screening study. It is divided into two portions. The safety portion is designed to determine the dose of the treatment agents. The expansion portion is designed to continue enrollment at the acceptable dose levels to determine efficacy of treatment in elderly (age 60+) newly diagnosed AML patients (Arm A: AZD1775 days 1-5 & 8-12) and AraC days 1-5 & 8-12) and to make a selection of one of the two randomized arms for Relapsed/Refractory AML and HMA failure MDS patients (Arm B: AZD1775 days 1-5 & 8-12) and AraC days 1-5 & 8-12; Arm C: AZD1775 days 1-5, 8-12, 15-19, 22-26).

The purpose of this screening design is NOT TO ensure a high probability that the very best treatment is selected, but to ensure a low probability that a poor treatment is selected. In other words, at the conclusion of this trial, we cannot make a definitive conclusion about the superiority of one treatment compared to the other, but we can ensure that there is a small probability of bringing the inferior treatment forward.

- 16.2 Statistical Design and Analysis for the Primary Endpoint
 - 16.21 Primary Endpoint

The primary endpoint of this trial is the rate of complete response (CR plus CRi). Throughout Section 16.0, complete response will be considered synonymous with "success", unless specified otherwise. All patients meeting the eligibility criteria, who have signed a consent form, and have begun treatment at the study MTD will be evaluable for complete response, with the exception of patients who are determined to be a major treatment violation.

Treatment Responses will be assessed by standard criteria for the respective disease per NCCN guidelines or according to specific criteria from expert panels (i.e. the International Working Group Criteria for the response in acute myeloid leukemias). Response will be assessed by peripheral blood criteria at the end of each cycle and every other cycle (for MDS) thereafter (Burnett et al. 2007. Gileset al. 2005, Kantarijian et al. 2012, Fenaux et al. 2009). Bone marrow tests to assess responses will be carried as outlined in the study tables

Bone marrow tests to assess responses will be carried as outlined in the study tables Table 4.1 and 4.2.

16.22 Arm A: Efficacy and safety of AZD1775 + AraC in elderly newly diagnosed AML

Statistical Design, Analysis and Decision Rule

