16.7 Early Safety Analysis

An early safety analysis will be performed after 6 patients have been accrued to each arm of the study and observed for one cycle. Accrual will be temporarily halted while these patients are evaluated. If 2 or more of the first 6 patients experience a DLT, as defined below, then the dose level will be reduced as defined in Section 8.0 and another six patients will be treated. If < 2/6 patients experience toxicities defined as DLT, then this dose level will be defined as the operational MTD and moved into the expansion portion. Further dose de-escalation to dose level -2 will follow the same guidelines.

Should additional modification be necessary, the study will be closed and evaluated by the study team regarding continuation. Upon determination of the safe dose level, the study will re-open for accrual.

16.8 Data & Safety Monitoring:

- 16.81 The principle investigator(s) and the study statistician will review the study at least twice a year to identify accrual, adverse event, and any endpoint problems that might be developing. The Mayo Clinic Cancer Center (MCCC) Data Safety Monitoring Board (DSMB) is responsible for reviewing accrual and safety data for this trial at least twice a year, based on reports provided by the MCCC Statistical Office.
- 16.82 Adverse Event Stopping Rules: To be evaluated in each arm independently, the stopping rules specified below are based on the knowledge available at study development. We note that the Adverse Event Stopping Rule may be adjusted in the event of either (1) the study re-opening to accrual or (2) at any time during the conduct of the trial and in consideration of newly acquired information regarding the adverse event profile of the treatment(s) under investigation. The study team may choose to suspend accrual because of unexpected adverse event profiles that have not crossed the specified rule below.

Accrual will be temporarily suspended to this study if at any time we observe events considered at least possibly related to study treatment (i.e. an adverse event with attribute specified as "possible," "probable," or "definite") that satisfy one of the following:

- if 3 or more patients in the first 10 treated patients in each arm experience a grade 4 or higher non-hematologic adverse event at least possibly related to treatment.

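### Section 7.22 fixes AraC at 20 mg twice daily in the expansion and ties only AZD1775 to the MTD, so a pass at default level -1 would return new patients to the dose pair just rejected

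*Combined protocol and SAP*

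**What the plan says.** The starting-dose table in Section 7.22 (expansion, Arms A and B) gives AZD1775 as the MTD and AraC as 20 mg SC twice daily. Its first footnote describes AraC as "a fixed dose of 20 mg s.c. per a single dose twice daily. In individual cases, a 10 mg/m² not to exceed 20 mg". Nothing in Section 7.22 links the AraC dose to the result of the safety portion.

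Other sections treat the two drugs as one level:

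- Section 7.73, after six patients at a level: "if DLT is observed in 1 or less patients, then the combination dose will be considered safe for the expansion phase".
- Section 16.7, for a level with fewer than 2 of 6 patients with DLT: "this dose level will be defined as the operational MTD and moved into the expansion portion".
- Section 16.1: "The safety portion is designed to determine the dose of the treatment agents" and "The expansion portion is designed to continue enrollment at the acceptable dose levels".
- Section 1.5: "The study will continue to enroll the rest of the patients at the tolerated dose".

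Section 7.21 sends a starting dose that is not tolerated to a lower combination in Table 8.11. Section 8.1 says that reductions generally fall on AraC first.

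**The concern.** The default first step down changes AraC only, and AraC is the drug that Section 7.22 holds constant. After a pass at that step, the AZD1775 part of the MTD is still 200 mg. A site writing orders from the Section 7.22 table would then restore the pair that had just failed the safety rule. The conflict arises only after a toxicity signal has forced a de-escalation.

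The primary analysis is also touched. Section 16.21 counts patients who began treatment at the study MTD. Expansion patients started on another pair would be pooled with six patients treated at the level that was cleared, and their evaluability could be questioned.

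**Working it through.** **1. Pair given by Section 7.22 for each level that could pass.** AZD1775 is taken from the passing level and AraC is 20 mg twice daily.

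| Level that passes (Table 8.11) | Cleared pair (AZD1775 daily + AraC) | Pair under 7.22 | Result |
|---|---|---|---|
| 0 | 200 mg + 20 mg twice daily | 200 mg + 20 mg twice daily | agrees |
| -1, default | 200 mg + 10 mg twice daily | 200 mg + 20 mg twice daily | the rejected level 0 pair |
| -1, footnote 1 | 100 mg + 20 mg twice daily | 100 mg + 20 mg twice daily | agrees |
| -2 | 100 mg + 10 mg twice daily | 100 mg + 20 mg twice daily | twice the cleared AraC dose |
| -2, footnote 2 | 100 mg + 10 or 20 mg once daily | 100 mg + 20 mg twice daily | 4 or 2 times the daily AraC dose (40 mg against 10 or 20 mg) |
| -1a | 150 mg, no AraC dose printed | 150 mg + 20 mg twice daily | agrees if cleared with 20 mg twice daily; doubles AraC if cleared with 10 mg twice daily |

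Over the 10 dosing days of a cycle, default level -1 gives 10 × 2 × 10 = 200 mg of AraC. Section 7.22 gives 20 × 2 × 10 = 400 mg.

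**2. The body-surface option.** At an assumed 1.5 to 2.0 m², 10 mg/m² gives 15 to 20 mg per dose, which is 1.5 to 2.0 times the 10 mg of level -1. It equals 10 mg only at 1.0 m².

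**3. Chance of a mismatch in one arm.** The documents give no DLT rate for this combination, so p = 10%, 20%, 30% and 40% are assumed. A level fails with 2 or more DLTs in 6:

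f(p) = P(Binomial(6, p) ≥ 2) = 1 − (1−p)^6 − 6p(1−p)^5

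The 3+3 path in Sections 7.72 and 7.73 gives the same values, because 2 or more DLTs in the first 3 patients already means 2 or more in 6.

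- Case (a): level 0 fails, then default level -1 passes. The chance is f(p) × (1 − f(p)) if the rate is unchanged at -1, or f(p) × (1 − f(p/2)) if it halves.
- Case (b): levels 0 and -1 fail, then level -2 passes. The chance is f(p)² × (1 − f(p)) if the rate is unchanged, or f(p) × f(p/2) × (1 − f(p/2)) if it halves at -1 and stays there at -2.

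| Quantity | p = 10% | 20% | 30% | 40% |
|---|---|---|---|---|
| f(p), level 0 fails | 0.1143 | 0.3446 | 0.5798 | 0.7667 |
| (a), rate unchanged | 0.1012 | 0.2259 | 0.2436 | 0.1789 |
| (a), rate halved | 0.1105 | 0.3053 | 0.4502 | 0.5025 |
| (b), rate unchanged | 0.0116 | 0.0778 | 0.1413 | 0.1371 |
| (b), rate halved | 0.0036 | 0.0349 | 0.1006 | 0.1732 |
| (a) or (b), rate unchanged | 0.1128 | 0.3037 | 0.3849 | 0.3160 |
| (a) or (b), rate halved | 0.1141 | 0.3401 | 0.5509 | 0.6757 |

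For example, at p = 30% with the rate halved, case (a) is 0.5798 × (1 − 0.2235) = 0.4502. The first row is an upper bound on any mismatch in that arm. The case rows give no weight to the footnote variants or to level -1a.

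**4. Patients exposed.** Section 16.3 places 15 Arm A and 14 Arm B patients in the expansion, on top of six per arm treated at the MTD. The shares are 15/21 = 0.71 and 14/20 = 0.70 of evaluable patients.

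**5. The plan's own operating characteristics.** For Arm A, P(Binomial(21, p) ≥ 6) is 0.083 at 0.15 and 0.904 at 0.40, against the printed 0.08 and 0.90. For Arm B, P(Binomial(20, p) ≥ 3) is 0.075 at 0.05 and 0.909 at 0.25, against 0.08 and 0.91. These figures reproduce and do not depend on the dose.

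**The case against.** The strongest reply is that the governing rule is already stated in Sections 1.5, 7.73, 16.1 and 16.7, so harm needs both a de-escalation and a site that follows one table cell against all of them. That lowers the likelihood. It leaves the printed starting dose unchanged.

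Other text helps less than it might seem:

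- Section 16.7 sends the cohort step-down to Section 8, so Section 8 does set first-cycle doses for new safety cohorts. For treated patients, however, Section 8.0 says "Dose modifications apply to the treatment given in the preceding cycle", and a new expansion patient has no preceding cycle. Section 15.24 mentions Section 8 adjustments but still starts AraC at 20 mg twice daily.
- The instruction to "call the MCCC Registration Office for dose level" stands in Section 6.1 for the safety portion. Section 6.2, for the expansion, does not repeat it.
- The Section 16.7 halt ends once a safe level is found. The stopping rule in Section 16.82 and the twice-yearly reviews could cut an error short, so 15 and 14 patients are ceilings.

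The points about size stand in part. Only case (a) restarts a rejected pair. Case (b) gives the footnote 1 pair, which was neither cleared nor rejected. No document supports a halved DLT rate. Section 7.4 excludes most myelosuppression from DLT, so the higher rates may not apply, and toxicity attributed to AZD1775 would lead to the footnote 1 route, where there is no conflict. Section 1.41 reports no DLTs on monotherapy and rates below 30% at the combination MTDs in PN001, so the 40% column is weakly grounded.

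**Conclusion.** The concern holds. The AraC entry in Section 7.22 is the outlier and is wrong as written on the default de-escalation path. The central case is a pass at default level -1, where the printed dose restores the rejected pair. Its chance in one arm is 0.10 to 0.24 with an unchanged DLT rate, or 0.11 to 0.50 with a halved rate. Both ranges assume DLT rates of 10% to 40%, use of the default steps only, and sites that follow Section 7.22. No conflict arises if level 0 or the footnote 1 variant passes. The harm is to patient safety and to the meaning of treatment at the MTD; the sample size, decision rules and power stand. Because the error takes effect only after a safety signal and is corrected by wording, it must be fixed.

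**What to change.** In Section 7.22, replace both dose entries with a statement that both agents are given at the dose level declared for that arm under Sections 7.73 and 16.7. Refer to Table 8.11, including any footnote variant or level -1a actually cleared. Let the 10 mg/m² footnote apply only when the cleared AraC dose is 20 mg twice daily. In Section 16.21, add a clause that the study MTD means that two-agent level, as a clarification in line with Section 16.7. Section 15.24 can stay as it is, because it already refers to Section 8.

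The choice of dose remains with the clinical team. The cost is wording in one dose table and its first footnote, plus one clause in Section 16.21. No patients, visits or procedures are added.
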